11.7.2 Secondary Efficacy Endpoint

11.7.2.1 Proportion of Subjects Achieving Glycemic Control

The following secondary efficacy variables will be analyzed using the 90% CI of difference of proportions:

- The number and percentage of subjects who achieve a FBG test result of ≤ 8.0 mmol/L (≤ 144.0 mg/dL) at visit Week 26
- The number and percentage of subjects who achieve a HbA1c of $< 7.0\%$ at visit Week 26.

The difference in proportions will be estimated along with the corresponding 90% CI in the FAS using a logistic regression model. Only measurements under treatment will be considered. Subjects without values available at week 26 will be considered as having not achieved glycemic control.

Additionally, number and percentages of subjects who achieve an FBG test result of ≤ 8.0 mmol/L (≤ 144.0 mg/dL) and number and percentages of subjects who achieve a HbA1c of $< 7.0\%$ will be presented by time point and treatment group.

Sponsor: Gan & Lee Pharmaceuticals, USA Corporation
Protocol no: GL-GLAT2-3002

Statistical Analysis Plan
Version Date: 16-Nov-2020

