### 8.4.1 Inclusion Criteria

Subjects must satisfy all of the following entry criteria before they will be allowed to participate in the study:

1. Male or nonpregnant, nonlactating female subjects between the ages of 18 and 75 years, inclusive
2. Ability to provide written, personally signed, and dated informed consent to participate in the study, in accordance with the ICH GCP Guideline E6 and all applicable regulations, before initiating any study-related procedures
3. Ability to understand and fully comply with all study procedures and restrictions.
4. Subjects with a confirmed diagnosis of type 2 diabetes mellitus who meet one of the following:
  - a. If insulin-naïve, subjects should have been on at least 2 approved OAMs for at least 12 weeks before screening, and the clinician has decided to add insulin therapy
  - b. If already being treated with a basal insulin, subjects should have been treated with insulin for at least 6 months in addition to at least 1 approved OAM, and must not have changed the type or brand of insulin within 6 months prior to screening
5. HbA1c values as follows:
  - a. If insulin-naïve, HbA1c ≤ 11.0%
  - b. If previously on a basal insulin regimen, HbA1c ≥ 7.0% and ≤ 11.0%
6. Body mass index (BMI) ≤ 45 kg/m^2
7. Adherence to a prudent diet and exercise regimen recommended by the medical provider, and willingness to maintain these consistently for the duration of the study

8. Concomitant medications are allowed, provided that no significant dosing changes are anticipated during the study (see the exclusion criteria below and [Appendix 3 \[Section 17.3\]](#) for specific allowed and prohibited concomitant medications); for concomitant thyroid medications, subjects must have been on a stable dosage for 90 days before screening

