**Table 3: Basal Insulin Dose Adjustment Based on Fasting Glucose Result**

Lowest Average Fasting Plasma Glucose (Pre-Breakfast) Value for 3 Days	Adjust Basal Insulin Dose (Units per Dose)
> 271 mg/dL (> 15.1 mmol/L)	+ 6 U
181 – 270 mg/dL (10.1 – 15.0 mmol/L)	+ 4 U
151 – 180 mg/dL (8.4 – 10.0 mmol/L)	+ 2 U

Lowest Average Fasting Plasma Glucose (Pre-Breakfast) Value for 3 Days	Adjust Basal Insulin Dose (Units per Dose)
131 – 150 mg/dL (7.3 – 8.3 mmol/L)	+ 1 U
71 – 130 mg/dL (> 3.9 – 7.2 mmol/L) (Target Level)	Maintain Current Dose
56 – 70 mg/dL (3.1 – 3.9 mmol/L)	- 2 U
< 56 mg/dL (< 3.1 mmol/L)	- 4 U

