### **12.9.3 Efficacy**

#### **12.9.3.1 Proportion of Subjects Achieving Glycemic Control**

The following secondary efficacy variables will be analyzed using a test of difference of proportions based on normal approximation and CIs:

- The number and percentage of subjects who achieve an FBG test result of  $\leq 8.0$  mmol/L ( $\leq 144.0$  mg/dL) at visit Week 26
- The number and percentage of subjects who achieve a HbA1c of  $< 7.0\%$  at visit Week 26

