11.8.5 Electrocardiograms

Values and change from baseline in ECG results will be summarized by time point and the treatment group. Descriptive statistics will be shown for baseline and visit Week 26. Potentially clinically significant ECG results will be summarized and will include the following categories:

- Heart rate < 50 beats per minute
- Heart rate > 100 beats per minute
- PR Interval \geq 200 msec
- QRS Interval \geq 200 msec
- QT Interval \geq 200 msec
- QT Interval change from baseline \geq 30 msec - < 60 msec
- QT Interval change from baseline \geq 60 msec
- Corrected QT using Fridericia's formula (QTcF) Interval \geq 450 - < 480 msec
- QTcF Interval \geq 480 - < 500 msec
- QTcF Interval \geq 500 msec
- Corrected QT using Bazett's formula (QTcB) Interval \geq 450 - < 480 msec
- QTcB Interval \geq 480 - < 500 msec
- QTcB Interval \geq 500 msec

where $QTcF = QT / [(heart\ rate/60)^{(1/3)}]$ and $QTcB = QT / [(heart\ rate/60)^{(1/2)}]$.

A listing of the observations with potentially clinically significant ECG results will be provided.

12. Validation

PRA's goal is to ensure that each TFL delivery is submitted to the highest level of quality. Our quality control procedures will be documented separately in the study specific quality control plan.

13. References

1. Chow, S-C, Shao, J. A note on statistical methods for assessing therapeutic equivalence. *Controlled Clinical Trials*. 2002; 23(5):515-520.
2. East 6 (2020). Statistical software for the design, simulation and monitoring clinical trials. Cytel Inc., Cambridge MA.
3. American Diabetes Association Issues Hypoglycemia Position Statement. American Diabetes Association Website. <https://care.diabetesjournals.org/content/diacare/early/2016/11/09/dc16-2215.full.pdf>. Diabetes Care. ePublished November 21, 2016.

Gan & Lee Pharmaceuticals USA

PRA HEALTH SCIENCES

Sponsor: Gan & Lee Pharmaceuticals, USA Corporation
Protocol no: GL-GLAT2-3002

Statistical Analysis Plan
Version Date: 16-Nov-2020

5. Matts, JP and Lachin, J M. 'Properties of permuted-block randomization in clinical trials', *Controlled Clinical Trials*. 1988, 9(4): 327–344.

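### Adding the baseline value to the Week 26 glycemic-control responder models (SAP 11.7.2.1) would gain precision at almost no cost, and the rates should be read as Week 26 status, not as new attainment of control

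*SAP*

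**What the plan says.** SAP 11.7.2.1 defines two responder endpoints as states at Week 26: "The number and percentage of subjects who achieve a HbA1c of $< 7.0\%$ at visit Week 26", and the matching one for FBG at or below 8.0 mmol/L (144 mg/dL). Neither depends on where the subject started. For the analysis it says: "The difference in proportions will be estimated along with the corresponding 90% CI in the FAS using a logistic regression model". No model terms are listed. Only on-treatment values count, and "Subjects without values available at week 26 will be considered as having not achieved glycemic control". The section also promises both responder rates by time point and treatment group.

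Protocol 12.9.3.1 describes the same comparison without covariates: "The following secondary efficacy variables will be analyzed using a test of difference of proportions based on normal approximation and CIs".

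On entry, Protocol 8.4.1 criterion 5a reads "If insulin-naïve, HbA 1c ≤ 11.0" percent, with no lower limit. The 7.0% floor in 5b covers only subjects previously on basal insulin. There is no FBG entry limit. Protocol 8.5.8.1 has basal-insulin subjects titrated for two weeks before randomization using Table 3, whose no-change band is "71 – 130 mg/dL (> 3.9 – 7.2 mmol/L) (Target Level").

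By contrast, the key secondary HbA1c analysis (SAP 11.7.1.1) adjusts for baseline HbA1c.

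**The concern.** Two things stand out. First, a responder analysis headed as achieving control counts anyone below the cut at Week 26, including subjects below it on Day 1. A reader of the report may take the rate as the share of patients the product brought to control, which it is not.

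Second, the baseline value is likely to be the best single predictor of being under the cut at Week 26, and the plan does not use it. The SAP moved from the Wald method to logistic regression for the primary endpoint (SAP 3.1) and uses logistic regression here too. Without a covariate that move changes nothing in the estimate or its interval. Randomization is unstratified (SAP 5.2), so a chance imbalance in subjects already at target goes into the unadjusted difference as noise that adjustment would largely remove.

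At stake are the width of two secondary confidence intervals and the wording of two secondary results.

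**Working it through.** **The plan's own figure.** No power, margin or expected rate is given for these endpoints. The only power claim is for the primary endpoint: 30% rate, 12% margin, 275 per arm. SE = √(2 × 0.30 × 0.70 / 275) = 0.0391, and power = 2Φ(0.12/0.0391 − 1.645) − 1 = 84.6%, against the stated 85%. It reproduces. It confirms 275 per arm as the basis but says nothing about the responder endpoints.

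**Is the model treatment-only?** SAP 11.7.2.1 is silent. The primary model's code is `model response=trt` (SAP 11.6.1.1). SAP 11.6.2.2, 11.6.2.4, 11.6.2.5 and 11.7.3.3 each state that treatment is the sole independent variable. Protocol 12.9.3.1 is unadjusted. Treatment-only is the natural reading.

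**What that model delivers.** In each arm the variance of the fitted logit is 1/[n·p(1−p)]. The delta method multiplies by [p(1−p)]², giving p(1−p)/n. Summed over arms, this is exactly the Wald variance.

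**Who can already be at target?**

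| Endpoint | Baseline value | Who can be at target |
|---|---|---|
| HbA1c <7.0% | Screening (not measured on Day 1) | Insulin-naïve subjects; entry deviations; possibly bolus-only subjects, whom synopsis criterion 4b admits and for whom criterion 5 sets no HbA1c range |
| FBG ≤144 mg/dL | Day 1, after titration | Any subject; the no-change band of 71–130 mg/dL lies inside the cut |

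The documents give no shares. Illustration for HbA1c: assume 20–50% insulin-naïve with baseline mean 8.3% and SD 1.2. The naïve share below 7.0% is Φ((7.0 − 8.3)/1.2) = 0.139. Overall that is 0.20 × 0.139 = 2.8% to 0.50 × 0.139 = 7.0%.

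**Does this shrink the arm difference?** With a share f at target at baseline:

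RD(all) = f × RD(at target) + (1 − f) × RD(not at target)

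Assume 8 points in subjects not at target:

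| RD at target | f = 10% | f = 50% |
|---|---|---|
| 0 points | 7.2 | 4.0 |
| 8 points | 8.0 | 8.0 |
| 12 points | 8.4 | 10.0 |

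The direction depends on a quantity the documents do not fix. Simulations with assumed inputs show the same:

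- HbA1c, about 12% below 7.0% at baseline, true shift 0.4%: 12.8 points in all subjects, 12.0 in those at or above 7.0%, 19.0 in those below. Including subjects at target widened the difference.
- HbA1c, the 20–50% naïve inputs above with 15% scored as failures: 13.0–13.3 points in all subjects, 13.1–13.3 in those not at target.
- FBG, baseline mean 140–180 mg/dL, SD 45, correlation 0.3–0.5, shift 10 mg/dL, 21–54% at target: 8.7–8.8 points in all subjects, 8.1–8.9 in those not at target.

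**Does adjustment move the estimate?** No. With a 0.4% shift the difference was 12.84 points both ways; with 0.2%, 6.67 unadjusted and 6.66 adjusted.

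**What does adjustment gain?** All for HbA1c, 275 per arm:

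- The 20–50% naïve inputs (other subjects mean 8.5%, SD 1.0, truncated at 7.0%; slope 0.5; residual SD 0.85), no treatment effect: variance down 10–13%. SE gain: 1 − √0.90 = 5% to 1 − √0.87 = 7%.
- The same inputs with a treatment effect and 15% scored as failures: variance down 12–16%, SE 6–8%.
- The scenario with about 12% at target: mean SE from 3.60 to 3.24 points, and from 3.76 to 3.38. Variance: 1 − (3.24/3.60)² = 19%. The spread of the estimates across trials fell from 3.65 to 3.35, or 1 − (3.35/3.65)² = 16%, so 19% is the upper end.

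**Chance imbalance, FBG illustration.** If 40% are at target, the SD of the between-arm difference in that share is √(2 × 0.4 × 0.6 / 275) = 4.2 points. If they respond 40 points more often, a one-SD imbalance moves the difference by 0.40 × 4.2 = 1.7 points.

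**The case against.** A reader might infer that counting subjects already at target pulls the arms together and so makes the products look similar. The documents do not support that. Subjects at target can lose control, and can do so differently by arm. Dilution requires that they differ less between arms than the rest, and nothing in either document says so. Randomization balances the at-target share in expectation, so the unadjusted difference is unbiased for Week 26 status in all randomized subjects.

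A reader might also call the rates inflated. They are only higher than a rate of new attainment, which is not the endpoint. The rules for missing and off-treatment values push the rates down.

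Other fair points on that side:

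- SAP 11.7.2.1 does not say the model is unadjusted; it says nothing. This stands as a matter of wording, and is itself a reason to state the terms.
- The cited reference, "Covariate-Adjusted Difference in Proportions from Clinical Trials Using Logistic Regression and Weighted Risk Differences" (SAP Section 13, reference 4), supports the delta-method standard error in 11.6.1.1. Its title commits the sponsor to no covariates. This stands.
- By-time-point tables include Day 1 (SAP Section 11), so the number at target at baseline should be visible per arm. This stands in part: marginal counts do not separate those who moved to target from those who stayed there, and they give no adjusted interval.
- Criterion 4a requires that the clinician has decided to add insulin, which makes a naïve subject below 7.0% less likely. This stands; the HbA1c overlap is probably small.
- These endpoints have no margin or success rule and are outside the testing hierarchy. This stands, and it sets the severity.

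**Conclusion.** The point holds as one of precision and interpretation, not of bias. A treatment-only model gives up roughly 10 to 16% of the variance of the HbA1c risk difference under the assumed inputs, and about 19% in the more favorable scenario. That is 5 to 10% in the width of the interval. No gain was simulated for FBG; it depends on how well Day 1 FBG predicts Week 26 FBG. The responder rates should be reported as the share at target at Week 26.

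Every size given here rests on assumed baseline distributions, since the documents provide none. That no baseline condition or covariate is named, and that some subjects can start at target, rests on the documents alone. Severity is low: the equivalence claims rest on AIA and on HbA1c change, and the latter already adjusts for baseline.

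**What to change.** In SAP 11.7.2.1:

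1. List the model terms: treatment and baseline HbA1c for the HbA1c responder model; treatment and baseline FBG for the FBG model, using the SAP 7.1 baseline definition.
2. Report the standardized risk difference: average the predicted probabilities over all FAS subjects under each treatment, take the difference, and give a delta-method 90% CI. This targets the same quantity as the unadjusted difference. Keep the unadjusted result as a supporting line.
3. State how a subject with no baseline value is handled, since the adjusted model would otherwise drop that subject.
4. Optionally, add a supportive comparison in subjects not at target at baseline (HbA1c ≥7.0%; FBG >8.0 mmol/L), with the number per arm already at target.
5. Describe the result as status at Week 26.

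The cost is a few lines of SAP text and code. The data are already collected and no visit changes. The optional subset is smaller than the FAS, so its interval will usually be wider, and it should stay descriptive.

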11.7.3 Exploratory Variables

11.7.3.1 Retrospective Hypoglycemic Rate

In addition to the analysis of hypoglycemic events from the AE data, a retrospective analysis of the CGM data will be performed to identify hypoglycemic events that may have gone unnoticed by the subject (Table 6, Analysis 1). A retrospective CGM-hypoglycemic event will be defined as anytime the glucose concentration decreases below the threshold of ≤ 3.0 mmol/L. This definition is supported by Seaquist et al (8). Multiple hypoglycemic events while a subject is wearing the CGM device may occur and are defined as having a glucose concentration that returns to > 3.0 mmol/L before decreasing below the threshold again. The number of hypoglycemic events detected between days 2 through 8 of CGM wear for each subject at each visit will be summarized descriptively in the SS. A listing of the CGM-hypoglycemic events including the lowest glucose concentration during the event will be provided.

11.7.3.2 Retrospective Time in Hypoglycemia/Hyperglycemia

The time in hypoglycemia/hyperglycemia/euglycemia will be summarized with descriptive statistics at each visit and overall using the SS (Table 6, Analysis 2).

11.7.3.3 Laboratory-Grade Hyperglycemia

Laboratory-Grade Hyperglycemia (LGH) is defined for any subject whose FBG result is strictly greater than 13.9 mmol/L (250 mg/dL). FBG is scheduled to be collected twice before randomization and at seven instances after randomization. The difference between treatment groups in the proportion of subjects who at any post-randomization time point with LGH will be estimated along with the corresponding 90% CI in the FAS using a logistic regression with treatment as the only independent variable in the model and reported with a p-value.

In addition, the number of incidences of LGH for each subject between visits 3 and 9 (post-randomization) will be counted. The difference between treatment groups in the mean number of LGH events will be estimated along with the corresponding 90% CI in the FAS using analysis of variance with treatment as the only independent variable in the model and reported with a p-value.

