5.1 Sample Size and Power

Enrollment was planned for 550 subjects overall (275 subjects per treatment group). The primary analysis for immunogenicity primary endpoint was to be an equivalence test for the difference in proportion of subjects who develop treatment-induced AIAs between Gan & Lee insulin Glargine Injection and Lantus® using the 2 Wald one-sided tests (TOST) approach with $\alpha=0.05$ (Chow and Shao 2002 (1)). After scientific and regulatory review, the method to evaluate immunogenicity equivalence will be the 90% confidence intervals of risk difference from logistic regression analysis (see Section 3.1). Under this newly adopted approach, no power loss is expected.

This sample size of 275 subjects per treatment group was chosen to achieve over 80% power using the TOST equivalence test for two proportions, a risk difference of zero and equivalence margins dependent on the observed treatment-induced AIA rate per Table 3 below. For example, a sample size of 550 will provide approximately 85% power for the TOST equivalence test using a treatment-induced AIA rate of 30% and a margin of 12% (See Table 3). The treatment-induced AIA is defined as newly confirmed positive AIA development or important (at least a 4-fold) increase in AIA titers, after baseline and up to visit Week 26 (see the definition of Primary Endpoint in Section 6.1 and Section 7.2). No drop outs are considered in the calculation. A larger than expected early discontinuation rate was observed as part of study monitoring activities and therefore protocol amendment 3 approved on 25-Apr-2019 included procedures to encourage subjects to return for assessments even if they have discontinued treatment early.

The appropriate similarity margin, based on the actual observed event rate for the intended reference product, will be used for final analysis after database lock as summarized in the Table 3 below. The power calculation in the table was adapted for a sample size of 550 using the treatment-induced AIA rate for the reference product. Linear interpolation will be used for values between AIA rates in the table.

Sponsor: Gan & Lee Pharmaceuticals, USA Corporation
Protocol no: GL-GLAT2-3002

Statistical Analysis Plan
Version Date: 16-Nov-2020

Table 3: Similarity margins for actual observed event rate of proposed biosimilar to insulin glargine for various immunogenicity event rates

Treatment-induced AIA Rate for the Reference Product	Margin	Power
10%	7.9%	83%
15%	9.3%	83%

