8.1 Full Analysis Set

The Full Analysis Set (FAS) comprises all subjects whose treatment was randomly assigned. Subjects in the FAS will be grouped according to planned treatment. Most efficacy endpoints will be analyzed using the FAS based on subject's randomized treatment and not administered treatment in case it differs.

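### Laboratory-grade hyperglycemia (SAP 11.7.3.3) is compared without regard to the number of fasting draws per subject, so unequal dropout could distort an exploratory comparison

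*SAP*

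**What the plan says.** SAP 11.7.3.3 defines LGH as a fasting blood glucose (FBG) result above 13.9 mmol/L (250 mg/dL) and notes that "FBG is scheduled to be collected twice before randomization and at seven instances after randomization". Two comparisons follow.

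- **Ever in LGH after randomization:** the difference in proportions with a 90% CI, "in the FAS using a logistic regression with treatment as the only independent variable in the model and reported with a p-value".
- **Number of LGH results:** "the number of incidences of LGH for each subject between visits 3 and 9 (post-randomization) will be counted". Then "The difference between treatment groups in the mean number of LGH events will be estimated" with a 90% CI, "in the FAS using analysis of variance with treatment as the only independent variable in the model and reported with a p-value".

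The section has no offset, no term for the number of draws, no minimum number of draws and no rule for missed samples. SAP 8.1 fixes who is included: "The Full Analysis Set (FAS) comprises all subjects whose treatment was randomly assigned".

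On dropout, SAP 5.1 states: "A larger than expected early discontinuation rate was observed as part of study monitoring activities". It gives no figure and no split by arm.

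**The concern.** An LGH event needs a blood draw to be seen. A missed draw can lower a subject's count or ever-LGH status, or leave it unchanged, but it can never raise it. A raw count therefore mixes how often glucose was high with how often it was measured.

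Three features of the plan make this more than a technicality:

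- Discontinuation was higher than expected.
- After stopping early, a subject has one further FBG only by attending the early-termination visit (Protocol 9.11, which repeats the Visit 9 procedures in 9.10). The later return visits at Weeks 12 and 26 are for antibody and HbA1c samples.
- Failure to respond adequately to study medication is a listed reason for withdrawal (Protocol 8.4.3.1), so stopping may be related to glucose.

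The SAP already handles the parallel problem elsewhere. In 11.8.1 it models hypoglycemia counts by negative binomial regression with log follow-up time as offset.

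At stake is whether a reported difference in LGH, with its p-value, reflects glycemia or the number of measurements. The distortion could also hide a real excess in the arm with more dropout.

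**Working it through.** **The plan's own figure.** The FBG row of Protocol Table 1 shows Weeks 2, 4, 8, 12, 16, 20 and 26 after randomization, which is seven draws, plus screening and Day 1 before. This agrees with SAP 11.7.3.3. The section states no power, LGH rate or dropout rate to reproduce.

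**Inputs.**
- From the documents: 275 per arm and seven draws for a completer.
- Assumed, because the documents give none: the same LGH risk per draw in both arms (mean p = 3%, 5% or 12%); beta-distributed variation between subjects with within-subject correlation ρ = 0.2; dropout d of 25% v 15% or 30% v 15%, unrelated to glucose; dropouts having 1 to 5 draws in total, equally likely (mean 3).

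**Step 1, draws and count ratio.** Mean draws = 7(1 − d) + 3d.
- d = 15%: 5.95 + 0.45 = 6.40
- d = 25%: 5.25 + 0.75 = 6.00
- d = 30%: 4.90 + 0.90 = 5.80

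Mean count = p × mean draws, so p cancels from the ratio: 6.00/6.40 = 0.94 and 5.80/6.40 = 0.91. Events per draw equal p in both arms, a ratio of 1.00. With equal dropout the raw ratio is also 1.00.

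**Step 2, size against sampling error.** For a subject with k draws, the variance of the count is k·p(1 − p)(1 + (k − 1)ρ). Averaging this over k and adding the variance of k·p gives the variance V per arm, and SE = √((V₁ + V₂)/275). With a = 4p and b = 4(1 − p) (since 1/ρ − 1 = 4), the chance of ever being in LGH over k draws is 1 − ∏(b + j)/(4 + j), j = 0 to k − 1. With B = bias/SE, two-sided 5% rejection is Φ(−1.96 − B) + 1 − Φ(1.96 − B).

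| LGH per draw | Dropout | Mean count | SE of difference | Bias in SE | Null rejection, count | Ever-LGH difference (points) |
|---|---|---|---|---|---|---|
| 3% | 25% v 15% | 0.180 v 0.192 | 0.053 | 0.23 | 5.6% | −0.55 |
| 3% | 30% v 15% | 0.174 v 0.192 | 0.053 | 0.34 | 6.4% | −0.83 |
| 5% | 25% v 15% | 0.300 v 0.320 | 0.068 | 0.29 | 6.0% | −0.87 |
| 5% | 30% v 15% | 0.290 v 0.320 | 0.067 | 0.45 | 7.3% | −1.30 |
| 12% | 25% v 15% | 0.720 v 0.768 | 0.102 | 0.47 | 7.6% | −1.68 |
| 12% | 30% v 15% | 0.696 v 0.768 | 0.101 | 0.71 | 10.9% | −2.53 |

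For ever-LGH the bias is 0.20 to 0.61 SE, with null rejection of 5.5% to 9.3%. The SAP gives no significance level for these p-values, so 5% is also an assumption.

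**Step 3, does the normal model itself fail?** In 20,000 simulated trials per setting with 20% dropout in both arms, the two-group test on the raw count rejected 4.9% of the time at each of the three risks. With unequal dropout at 12% risk it rejected 7.3% (25% v 15%) and 11.0% (30% v 15%), in line with the table. The excess comes from unequal draws, not from skewed counts.

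**Step 4, the early-termination draw.** Suppose instead that dropout is spread evenly over the seven intervals and every dropout attends that visit. Dropouts then average 4 draws, and mean draws are 6.25 v 6.55 (ratio 0.95) and 6.10 v 6.55 (ratio 0.93). The bias shrinks but remains.

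**Step 5, masking.** A true per-draw rate ratio of 1.15 in an arm with 30% v 15% dropout would appear as 1.15 × 0.906 = 1.04.

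**The case against.** The strongest reply is that nothing in the documents shows unequal dropout. SAP 5.1 reports only a pooled impression. A reader might infer that the arm with more dropouts will look better in this trial. The documents do not support that, because with equal, non-informative dropout the planned comparison is unbiased under the null. This stands, and the point is conditional on it.

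A reader might also infer that analysis of variance is invalid for counts with many zeros. Step 3 does not support that: with about 275 per arm and equal dropout, the error rate is nominal. The non-normality argument has no weight here.

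The early-termination visit gives an attending subject a fasting draw close to withdrawal. This softens the bias without removing it.

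The consequence is also limited. LGH sits under exploratory variables and is not among the exploratory endpoints in Protocol 8.8 or SAP 6.4. It has no margin or decision rule and lies outside the testing hierarchy. The disposition tables and the Kaplan-Meier plot of time to discontinuation (SAP 11.2) would show an imbalance. The Week 26 responder analysis (SAP 11.7.2.1) counts missing values as failures, which works against the arm with more dropout. All of this limits the importance of the point, but none of it puts the number of draws into the LGH models.

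**Conclusion.** The point holds as a cheap improvement to an exploratory analysis. As planned, both LGH comparisons ignore the number of draws and give no protection if discontinuation differs between arms, in amount or in its relation to glucose. Under the assumptions above, the raw count ratio is about 0.94 to 0.91 with no true difference, the bias is about 0.2 to 0.7 of a standard error, null rejection is about 6-11%, and ever-LGH differs by about 0.6 to 2.5 points. The LGH risks, the between-subject variation, the dropout split and the number of draws per dropout are all assumed. No primary or key secondary conclusion depends on this.

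A reader might infer that a per-draw model would also cure withdrawal caused by hyperglycemia. It would not. The offset corrects unequal numbers of draws, but not events lost because the subjects at highest risk left.

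**What to change.** In SAP 11.7.3.3:

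1. Replace the analysis of variance with negative binomial regression of the LGH count on treatment, with log(number of post-randomization FBG draws) as offset. An equivalent choice is to model LGH results out of draws taken, allowing for overdispersion. Report the rate ratio with its 90% CI. Baseline FBG may be added as a covariate but is not needed for this point.
2. Beside the ever-LGH comparison, show the distribution of post-randomization FBG draws by arm.
3. State that subjects with no post-randomization FBG are not scored as having zero events, and report their number by arm.
4. Note that dropout related to glucose remains a limitation of both comparisons.

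**Cost:** one changed model and one added table row, using data already collected. The hypoglycemia model in 11.8.1 supplies the pattern. The change should be made before database lock so that it is prespecified. **Downside:** the effect becomes a rate ratio instead of a difference in mean counts.
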